6.3.5 Day 28 of each cycle - Arm 3A patients only

All day 28 evaluations should be performed within 3 days before or 3 days after day 28 of the cycle.

- Physical examination including, but not limited to, WHO performance status and neurological evaluation
- Hematology (see section 6.2)
- Vital signs (see section 6.2)
- Assessment of all adverse events according to CTCAE 4.0

6.3.6 Every 8 weeks (+/- 7 days)

- Gadolinium-enhanced MRI. If PR, CR, an additional scan after 4 weeks should be done to confirm the response (as per chapter 4)
- Quality of life assessment, including EORTC QLQ-C30 and EORTC-BN20 at week 8 (+/- 7 days) and 16 (+/- 7 days) only (see section 10.1)

6.3.7 At end of treatment (35 days after last administration/infusion)

- Concomitant medications
- Assessment of all adverse events according to CTCAE 4.0
- For subjects assigned to ABT-414: Pharmacokinetic sample collection 35 days (\pm 2 day window) after last infusion for subjects able to return to the clinic (see table in section 6.3.2)
- Steroid intake

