5.2.2 Lomustine

Arm 3A: Patients relapsing during TMZ treatment or within the first 16 weeks after the first day of the last TMZ cycle will be treated with lomustine 110 mg/m² on day 1 of every 42-day treatment period. However, similar to subjects who are randomized to ABT-414 plus TMZ (Arm 1), ABT-414 (Arm 2) or TMZ control (Arm 3B), scans (MRI) should be performed as per the schedule outlined for all other arms (see section 6.3.5). Treatment will continue until one of the treatment withdrawal criteria has been met. Lomustine will be given for a maximum of one year.

The doses may be rounded to the nearest 40 mg to accommodate tablet strengths. The dose of lomustine does not have to be adjusted unless there has been at least a 10% change in body weight; recalculation of lomustine dose for < 10% weight changes is allowed at the discretion of the Investigator.

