5.5.2.1.1 Hematological toxicity

In general, the nadirs for hematological toxicity with lomustine are expected between days 28 and 35. In case of hematological toxicity grade 3 or 4 (according to CTCAE v. 4.0), the dosage of the next cycle will be reduced with one level. If the hematological toxicity does not recover within 4 weeks or if after recovery the hematological toxicity recurs at a subsequent cycle to grade ≥ 2 , lomustine treatment should be discontinued. No more than two dose reductions are allowed.

Administration of next cycle: If blood examination on day 42 or 43 (which may have been obtained in the prior 48 hours) show recovery of platelets above 100×10^9 and granulocytes counts above 1.5×10^9 , the next dose may be administered on day 43. If this is not possible, hematologic parameters will be repeated weekly and the next cycle will be given upon recovery of granulocytes and platelets. If after 4 weeks the patient has still not recovered, they should discontinue study treatment and stay on study until progression.

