6.3.8 At end of treatment (49 days after last administration/infusion)

- Concomitant medications
- Assessment of all adverse events according to CTCAE 4.0
- Steroid intake

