6.4 After end of treatment

Every 12 weeks (+/- 14 days) since last protocol treatment administration until death or loss to follow up:

- Survival follow up
- Further anti-cancer treatments/modalities
- Physical examination including WHO performance status and neurological examination
- Ocular examination if clinically indicated
- Vital signs if clinically relevant
- Steroid intake
- Concomitant medication collection if clinically relevant
- Assessment of all adverse events according to CTCAE 4.0 (i.e. for events not resolved after the end of treatment and new events related to study treatment)

If a subject is unable to return to the clinic for this visit, survival follow up and other assessments as appropriate may be completed via phone.

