11.4 Analysis of Laboratory, Vital Signs, and ECG Data

Biochemical parameters (serum creatinine, total bilirubin, AST, ALT, alkaline phosphatase, phosphate, total protein, albumin, sodium, potassium, calcium, and chloride) will be collected at baseline (all Arms), and Day 1 of each cycle (all Arms).

Hematological parameters (WBC, absolute neutrophil count, lymphocytes, hematocrit, hemoglobin, and platelet count) will be collected at baseline (all Arms), Day 1 of each cycle (all Arms), Day 14 of each cycle (Arms 1 and 2 only), Day 21 of each cycle (Arms 1 and 3B only), and Day 28 of each cycle (Arm 3A only).

Vital sign parameters (diastolic/systolic blood pressure, pulse rate, and body temperature (°C)) will be collected at baseline (all Arms), Day 1 of each cycle (all Arms), Day 14 of each cycle (Arms 1 and 2 only), and Day 28 of each cycle (Arm 3A only), and follow-up visit if clinically indicated/relevant.

Twelve-lead ECG data will be collected at baseline, immediately after ABT-414 dosing on Day 1 of Cycle 1 and Cycle 3 (Arms 1 or 2 only).

For hematological, biochemical, and vital sign parameters, changes from baseline are analyzed for each post-baseline visit (as specified in Section 6.0 Analysis of Conventions) and the final visit. If more than one measurement exists for a subject on a particular day, an arithmetic average will be calculated. The average will be considered to be the subject's measurement of that day. Descriptive statistics will be presented for baseline, each post-baseline, and the final visit by each treatment arm. Mean change from baseline to each post-baseline visit and the final visit within each treatment arm will also be presented. The highest and lowest values of each hematological parameter will be identified for each subject, and descriptive statistics for mean change from baseline within each treatment arm will be presented.

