11.4.2 Assessment of Hepatotoxicity

The number and percentage of subjects with maximum treatment-emergent laboratory values meeting the following criteria were summarized to assess potential hepatotoxicity.

Potential hepatotoxicity criteria defined in Hy's law:

- $\text{ALT} \geq 3 \times \text{ULN}$ and $\text{total bilirubin} \geq 2 \times \text{ULN}$

- $AST \geq 3 \times ULN$ and total bilirubin $\geq 2 \times ULN$
- ALT and $AST \geq 3 \times ULN$ and total bilirubin $\geq 2 \times ULN$

The maximum ratio relative to the ULN will be used to determine if subjects met the criteria listed above. The ALT, AST, and total bilirubin values do not need to be concurrent in order to meet the defined criteria as long as collected up to 35 days following the last dose date of study drug (ABT-414/TMZ/lomustine). For ALT, AST, and total bilirubin, a subject will be counted if the post-baseline laboratory value up to 35 days following the last dose date of study drug (ABT-414/TMZ/lomustine) met the above criteria regardless of the baseline laboratory value (i.e., the post-baseline laboratory value does not need to be worse than the baseline laboratory value).

A listing of all ALT, AST, total bilirubin, and alkaline phosphatase values will be provided for all subjects who meet any of the criteria defined above.

11.5 Analysis of Vital Signs Using Criteria for Potentially Clinically Significant Vital Sign Values

Vital signs values will be assessed for potential clinical significance through the application of criteria developed by the sponsor as detailed in [Table 10](#).

Table 10. Criteria for Potentially Clinically Significant Vital Sign Values

Vital Signs Variables	Criterion	Definition of Potentially Clinically Significant Values
Systolic blood pressure	High	Value ≥ 160 mmHg
Diastolic blood pressure	High	Value ≥ 100 mmHg
Heart rate	Low	Value ≤ 50 bpm
	High	Value ≥ 120 bpm
Temperature	Low	Value $\leq 32^\circ\text{C}$
	High	Value $> 40^\circ\text{C}$

The number and percentage of subjects with post baseline values meeting Criteria for Potentially Clinically Significant Vital Signs values will be summarized. The baseline will be defined as the last non-missing measurement collected prior to or on the first dose

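### No biochemistry is scheduled in any arm after day 1 of the last dosed cycle, although the SAP's laboratory tables accept values up to 35 days after the last dose

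*Protocol*

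**What the plan says.** **After the last dose.** Protocol 6.3.7, "At end of treatment (35 days after last administration/infusion", lists concomitant medication, adverse events, a PK sample for ABT-414 patients able to return, and steroid intake. Protocol 6.3.8, "At end of treatment (49 days after last administration/infusion", lists the same without the PK sample. Protocol 6.4, "Every 12 weeks (+/- 14 days) since last protocol treatment administration until death or loss to follow up", covers survival, further treatment, examinations, steroids and adverse events. None of the three lists hematology or biochemistry.

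**Within cycles.** Under Protocol 6.3.1, day-1 tests are done within 3 days before or on day 1, before dosing. SAP 11.4 says that biochemistry "will be collected at baseline (all Arms), and Day 1 of each cycle (all Arms"), and gives no other time. Hematology has extra times:
- Arms 1 and 2: about day 14, before or on the day of the second infusion.
- Arms 1 and 3B: day 21 ± 3, which may be omitted once the dose level has proved well tolerated.
- Arm 3A: day 28. Protocol 6.3.5 says "All day 28 evaluations should be performed within 3 days before or 3 days after day 28 of the cycle".

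**What the tables count.** SAP 11.4 takes the final shift grade from the last post-baseline value no later than 35 days after the last dose. SAP 11.4.2 accepts liver values "as long as collected up to 35 days following the last dose date of study drug".

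**Lomustine.** The dose is "lomustine 110 mg/m² on day 1 of every 42-day treatment period" (Protocol 5.2.2), and "the nadirs for hematological toxicity with lomustine are expected between days 28 and 35" (Protocol 5.5.2.1.1).

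**The concern.** The SAP's laboratory window extends past the last dose, but the visit schedule puts almost no safety blood test there. Liver tests are the clearest case. Protocol 1.7 reports transaminase elevations more often with ABT-414 than with control. Protocol 1.6 gives ABT-414 a terminal half-life of about 7.5 to 12 days, so exposure continues after the last infusion. Appendix L warns that drug-induced liver injury can appear or worsen once the drug has been withdrawn. A silent rise in transaminases will not come to light when the patient is asked about adverse events at day 35.

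Two things are at stake. The final grade may in practice be a value taken before the last dose. And the extent of the gap depends on cycle length and dosing days, so it differs between the arms that the safety tables set side by side.

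**Working it through.** The plan states no figure on this point, so the check is calendar arithmetic on the scheduled days. It uses the section text, because the schedule tables are partly broken in the available copy.

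**1. Biochemistry.** Inputs: last scheduled test on day 1 of the last dosed cycle; ABT-414 on days 1 and 15 of 28; TMZ on days 1 to 5 of 28; lomustine on day 1 of 42. The SAP window ends on the last dose day + 35.

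| Last dose | Window ends (cycle day) | Days from last scheduled biochemistry to window end | Next cycle's day 1, days after last dose |
|---|---|---|---|
| ABT-414, day 15 | 15 + 35 = 50 | 50 − 1 = 49 | 29 − 15 = 14 |
| ABT-414, day 1 | 1 + 35 = 36 | 36 − 1 = 35 | 29 − 1 = 28 |
| TMZ, day 5 | 5 + 35 = 40 | 40 − 1 = 39 | 29 − 5 = 24 |
| Lomustine, day 1 | 1 + 35 = 36 | 36 − 1 = 35 | 43 − 1 = 42 |

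The last column applies only if the next cycle's day-1 tests are drawn and dosing is then not given. On 28-day cycles such a value falls inside the 35-day window. On the 42-day lomustine cycle it does not: even drawn 3 days early, on day 40, it is 40 − 1 = 39 days after the dose. The lomustine day-28 visit repeats hematology but not biochemistry.

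**2. Hematology, Arm 2.** The day-14 count comes before or on the day of the second infusion. After a final day-15 infusion, the next scheduled count is day 1 of a cycle that is not given.

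**3. Hematology, lomustine.** The scheduled count is day 28 ± 3, that is days 25 to 31. The expected nadir is days 28 to 35. They overlap on days 28 to 31, which is 4 of 8 days. In a completed cycle the count is therefore taken after the dose and around the expected nadir.

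**4. A final cycle cut short.** The week-8 scan falls on day 7 × 8 + 1 = 57. With on-time lomustine dosing on days 1 and 43, that is cycle 2 day 57 − 42 = 15, or days 8 to 22 with the ± 7-day scan window. The count is not due until day 25 at the earliest. On 28-day cycles day 57 is cycle 3 day 1, so the cycle-2 TMZ count (28 + 21 = day 49) is already due.

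**5. How common stopping by then could be.** With exponential PFS and the plan's 2.6-month control median, 1 − exp(−ln 2 × (56/30.4375)/2.6) = 0.39 of control patients have a PFS event by week 8. The range is 0.33 to 0.47 for medians of 3.2 to 2.0 months. This is illustrative: it uses the mixed-control median and counts deaths as well as progressions.

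**The case against.** The case against has real force.

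- **The 35-day limits are upper bounds.** They say which values count and promise no sample at day 35. This stands: Protocol and SAP do not contradict each other.
- **The lomustine nadir is sampled.** A reader might infer that it goes unmeasured. The documents do not support that, because Arm 3A has a count around day 28 of each cycle, and Protocol 5.5.2.1.1 adds counts before the next dose.
- **Cycle-day tests need not lapse on stopping.** A reader might take the heading of Protocol 6.3 to mean that they do. But the same section contains the 35-day and 49-day visits, so its heading does not end at the last dose. The text is silent on truncated final cycles. On the other side, Protocol 5.4 sends patients who stop for toxicity, refusal or other reasons to the follow-up schedule, which has no laboratory tests. The ambiguity stands; a definite lapse does not.
- **Other monitoring exists.** Protocol 7.2.1 requires routine monitoring for clinical and laboratory evidence of adverse events, and Appendix L requires repeat testing and follow-up of liver abnormalities. Unscheduled tests will therefore supply some values. But Appendix L starts only once an abnormal result is known. The same holds for the adult hepatic table in Protocol 5.5.1.4, whose action column is blank in the available copy.
- **The consequence is limited.** Safety is descriptive, and the OS analysis is unaffected.

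None of this supplies a scheduled liver test after day 1 of the last dosed cycle.

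**Conclusion.** The point holds as a gap in scheduled safety sampling. Post-dose biochemistry for the last cycle depends on unscheduled tests in every arm, or on day-1 tests drawn for a next cycle that is then not given. Only on 28-day cycles can the latter fall inside the SAP window. Arm 2 also lacks a scheduled count after a final day-15 infusion. For lomustine and TMZ, the open question is whether the day-28 and day-21 counts remain due when the last cycle is cut short. A lomustine patient stopped at the week-8 scan is the plainest example.

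Two stronger sizes are tempting. For an ABT-414 patient stopped at day 57 after infusions on days 1, 15, 29 and 43, the window ends on day 43 + 35 = 78. A reader might infer that (78 − 29)/78 = 63% of it follows the last liver test. That assumes the cycle-3 day-1 tests, due by day 57, were not done; if they were, the share is (78 − 57)/78 = 27%. A reader might also multiply the 39% by an assumed number of lomustine patients. The documents give no PFS assumption for lomustine alone. The 39% also includes deaths: under the plan's 7-month OS median and exponential survival, 1 − 2^(−(56/30.44)/7) = 17% would have died by week 8. No patient count follows.

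The arithmetic assumes on-time dosing. This is a worthwhile, inexpensive improvement rather than an error as written.

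**What to change.** 1. Add the hematology and biochemistry panels of Protocol 6.2 to the 35-day end-of-treatment visit in all arms, and list that collection time in SAP 11.4.
2. State in Protocol 6.3.4 and 6.3.5 that the day-21 and day-28 counts of the final cycle are still due after discontinuation. For lomustine the 35-day visit is cycle day 36, just after the expected nadir, so it complements the day-28 count and does not replace it.
3. In SAP 11.4, report per arm how many patients have no hematology value, and how many have no biochemistry value, after their last dose.

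The cost is protocol and SAP wording plus one blood sample at a visit that already exists. PK blood is already drawn there in Arms 1 and 2; in Arm 3 it is a new draw. Patients unable to return will still lack the sample, and item 3 makes their number visible.

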6.3.8 At end of treatment (49 days after last administration/infusion)

- Concomitant medications
- Assessment of all adverse events according to CTCAE 4.0
- Steroid intake

6.3.9 At 6 months after randomization (+/- 1 month)

- Quality of life assessment, including EORTC QLQ-C30 and EORTC-BN20 (see section 10.1)

6.4 After end of treatment

Every 12 weeks (+/- 14 days) since last protocol treatment administration until death or loss to follow up:

- Survival follow up
- Further anti-cancer treatments/modalities
- Physical examination including WHO performance status and neurological examination
- Ocular examination if clinically indicated
- Vital signs if clinically relevant
- Steroid intake
- Concomitant medication collection if clinically relevant
- Assessment of all adverse events according to CTCAE 4.0 (i.e. for events not resolved after the end of treatment and new events related to study treatment)

If a subject is unable to return to the clinic for this visit, survival follow up and other assessments as appropriate may be completed via phone.

6.4.1 From end of study treatment until progressive disease

Every 8 weeks (+/- 7 days)

- Gadolinium-enhanced MRI. If PR, CR, an additional scan after 4 weeks should be done to confirm the response (as per chapter 4)

6.5 Summary table

	Before registration	Registration	Baseline 2 wks prior to randomization	Randomization				During protocol treatment, each cycle				Every 8 weeks	EoT ⁹	6 months after randomization	Follow-up			
				Day 1 ⁰	Day 14 Arm 1 & 2	Day 21 Arm 1 and 3B	Day 28 Arm 3A ¹⁴	Day 1 ⁰	Day 14 Arm 1 & 2	Day 21 Arm 1 and 3B	Day 28 Arm 3A ¹⁴				every 12 weeks			
PIS/IC for registration (EGFR)	X																	
Histology	X		X															
WHO Performance Status			X															X
Biological samples for central EGFR assessment	X																	
EGFR gene amplification			X															
Biological samples for TR projects (optional)			X															
PIS/IC for study			X															
Weight			X															
Medical his. & Demographic			X															
Whole blood for germline DNA and TR projects (optional)			X															
Prior anti-cancer therapies			X															
Physical examination ¹			X															X
Vital signs			X															X ¹⁰

	Before registration	Registration	Baseline 2 wks prior to randomization	Randomization	During protocol treatment, each cycle				Every 8 weeks	EoT ⁹	6 months after randomization	Follow-up every 12 weeks
					Day 1 ⁰	Day 14 Arm 1 & 2	Day 21 Arm 1 and 3B	Day 28 Arm 3A ¹⁴				
Quality of life assessment			X					X ⁸		X		
ECG			X									
Concomitant medication collection			X						X		X ¹⁰	
Steroid intake			X						X		X	
Prophylactic eye drops ¹⁵						X						
Adverse events (CTCAE v.4.0)			X						X		X ¹¹	
Hematology ²			X			X ⁷						
Biochemistry ³			X									
Serum/urine pregnancy test			X ⁴									
Plk samples									X ⁹			
PD samples												
PG samples (optional)												
Gd-MRI			X					X				
Survival and further anti-cancer treatments											X	

0 For day 1 of cycle 1, if the evaluations listed here have been already performed during the screening phase and within 2 weeks prior to this day 1, the same results can be used for cycle 1 and tests do not need to be repeated: physical examination including, but not limited to, WHO performance status and neurological evaluation; ocular examination if clinically indicated; hematology and biochemistry; vital signs; weight.

- 1 Physical examination including neurological evaluation, and ocular examination at baseline and if clinically indicated
- 2 Including WBC, absolute neutrophil count, lymphocytes, hematocrit, hemoglobin and platelet count
- 3 Including serum creatinine, total bilirubin, ASAT, ALAT, alkaline phosphatase, phosphate, total protein, albumin, sodium, potassium, calcium and chloride
- 4 Pregnancy test must be done within 72 hours prior to randomization
- 5 ECG only day 1 of cycle 1 and 3, immediately after the ABT-414 infusion and only for patient treated with ABT-414 (Arm 1 or 2)
- 6 PK samples to be collected at day 1 of ABT-414 cycles 1, 2, 3 and then every 2 ABT-414 cycles (Day 5 samples will only be collected during cycles 1 and 2)
- 7 Hematology at day 21 can be omitted once treatment at the present dose level caused only grade 1 or less hem. toxicity at day 21 and only grade 2 or less at day 28
- 8 QoL only at week 8 and week 16 while on treatment
- 9 End of Treatment visits 35 days and 49 days after last protocol drug administration. PK samples to be drawn at 35 days after last protocol drug administration only.
- 10 If clinically indicated / if clinically relevant
- 11 Assessment of AEs not resolved after EOT or AEs related to study treatment
- 12 PD samples to be collected at day 1 of cycles 1, 2 and 3 and only for patient in an ABT-414 arm (Arm 1 or 2)
- 13 PG sample optional, to be collected at day 1 of cycle 1 or it may be collected anytime during the study
- 14 Repeat physical examination including WHO performance status and neurological evaluation, hematology, vital signs and adverse event assessments at day 28 for patients in the lomustine arm (Arm 3A)
- 15 Prophylactic steroid ophthalmic solution prior to each infusion of ABT-414; 2 drops in each eye every 8 hours to start 48 hours prior to ABT-414 dosing and continue for a total of 7 days

7 Criteria of evaluation

7.1 Evaluation of activity

7.1.1 General method of response assessment

Response to treatment is assessed on the basis of a set of target lesion(s) chosen before the first treatment administration (the complete list of target lesions must be reported on the initial measurement form before the start of treatment). These lesions must initially be measured in their two perpendicular dimensions, and these measurements must be repeated at each evaluation of the disease by the same method. Response evaluation is based on neuro-radiological imaging (MRI). For this protocol objective response (complete, partial response) and progression will be assessed by MRI (see section 7.1.1.4). Objective response will only be assessed in patients not having undergone second surgery with complete removal of contrast enhancing lesions prior to study entry. For these patients measurable disease is required, which is defined as a clearly enhancing tumor with at two perpendicular diameters at entry equal or superior to 1 cm.

The contrast enhancing area will be considered as the basis for the tumor size assessment. Tumor size is defined as the product of the two largest perpendicular diameters. For evaluating partial and complete response, the baseline scan must be used for initial comparison. In initially responding ($\geq 50\%$ reductions in cross-sectional areas) or stabilized ($< 50\%$ reduction and $< 25\%$ increase in cross-sectional areas) patients, new scans must be compared to the nadir, this is the scan showing the maximum response (i.e. minimum tumor size) during or after treatment. In assessing response, changes on T2 weighted images must be taken into consideration.

